4.4 Treat to target approach in IBD treatment

"Treat to target" approach - evidence- and consensus-based recommendations for selecting the goals for treat-to-target strategies in patients with IBD. A "Treat to target" approach for UC includes clinical remission (defined as resolution of rectal bleeding and diarrhea/ altered bowel habit) and endoscopic remission (defined as Mayo endoscopic subscore of 0–1). Biomarker remission (normal C-reactive protein (CRP) and calprotectin) is considered as an adjunctive target. Histological remission is considered as an adjunctive goal [17, 21].

Clinical remission for CD is defined as resolution of abdominal pain and diarrhea/ altered bowel habit. Endoscopic remission for CD is defined as resolution of ulceration at ileocolonoscopy or resolution of findings of inflammation on cross-sectional imaging in patients who cannot be adequately assessed with ileocolonoscopy. Biomarker remission (normal C-reactive protein (CRP) and faecal calprotectin) is considered as an adjunctive target [14, 21].

Treat to target approach achievement will be evaluated at observational (Month 6) and final (Month 12) visits.

5 Introduction

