Augmentation with non-biological therapy will be defined as starting a new non-biological drug or increase in dose/frequency of the concurrent non-biological drugs with biological therapy. Non-biological therapies included aminosalicylates, immunomodulators, and corticosteroids;

Switching will be defined as a subset of initial biologic agent discontinuers who initiated another biological therapy;

IBD-related surgery will include but not be restricted to colectomy, ostomy (colostomy or ileostomy), fistula repair, abscess repair, and strictureplasty.

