### 5.3.3 Collection of data on the continuous basis

All data described below should be collected through whole observational prospective 1-year period of patients within the periods: Baseline visit -Visit 2, Visit 2 - Visit3 (independently of actual number of patient's visit to the clinic):

- IBD treatment;
- IBD surgical treatment (indications, types of surgeries, complications, presence of stoma, etc.);
- Results of diagnostic methods used (within the period since last visit);
- Healthcare resources utilization;
- Concomitant treatment;
- Adverse events and adverse drug reactions (seriousness, severity, causality, start and stop dates, action, frequency, outcomes):
  - adverse drug reactions on IBD treatments, ○ adverse events on Entivyo® (Vedolizumab) treatment,
  - serious adverse events on IBD treatments (including Entivyo® (Vedolizumab) treatment).

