#### Secondary endpoints (outcomes):

- Distribution of socio-demographic variables in patients with moderate to severe UC/CD treated with biologics or/and non-biological treatment;
- Distribution of clinical variables in patients with moderate to severe UC/CD treated with biologics or/and non-biological treatment. Clinical characteristics include family history of IBD, smoking habits (no smoker, ex-smoker and current smoker), medical history comorbidities, disease characteristics (age of disease onset, location of disease, clinical course, disease severity, intestinal and systemic (extraintestinal) manifestations, complications in history and during the study observational period, etc.);
- Description of methods used for documentation of disease activity in routine practice (incl. clinical, endoscopic, lab, histological), and frequency of objective CD/UC disease activity assessment using different methods;
- Percentage of moderate to severe IBD patients achieved clinical and combined clinical and endoscopic remission (based on T2T definitions);
- Percentage of patients with moderate to severe IBD with at least one episode of failure of biological therapy or/and non-biological therapy (e.g., dose escalation of biologics, switching to another therapy, IBD-related surgery, medication augmentation);
- Patterns of treatment decisions\actions made after making the clinical assessment of IBD activity (incl. therapeutic de-escalation, escalation, without changes) depending on scenario of achievement /non-achievement of T2T treatment goals;
- Challenges of implementing a T2T strategy in UC and CD in real clinical practice (incl. clinicians related factors, patient related factors, disease related factors);
- Healthcare resources utilization for patients with moderate to severe UC/CD: hospitalizations due to complications, IBD related surgeries, disability determination

Protocol ID	MACS-2017-102279	STATISTICAL ANALYSIS PLAN	Page 16 of 41	
IP	N/A		Date	30.12.2021
ID	MACS-2017-102279_SAP		Version	v1.2 final

(frequency, percentage of UC and CD patients, who used these healthcare resources) within 2 years before enrolment and during 12-months observational period;

- Percentage of UC and CD patients with surgical treatment in 2 years history and during 12-months observational period in frames of this study: indications, types of surgeries, complications.

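### Treat-to-target remission carries no condition on surgery, so a remission reached after bowel resection is credited to the therapy that preceded the operation

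*Protocol*

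**What the plan says.** Protocol 4.4 sets the T2T definitions. For UC they are "clinical remission (defined as resolution of rectal bleeding and diarrhea/ altered bowel habit" and "endoscopic remission (defined as Mayo endoscopic subscore of 0–1". For CD: "Clinical remission for CD is defined as resolution of abdominal pain and diarrhea/ altered bowel habit", and "Endoscopic remission for CD is defined as resolution of ulceration at ileocolonoscopy or resolution of findings of inflammation on cross-sectional imaging", the imaging route being for patients whom ileocolonoscopy cannot adequately assess. On timing: "Treat to target approach achievement will be evaluated at observational (Month 6) and final (Month 12) visits".

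SAP 6.1 makes this a secondary outcome: "Percentage of moderate to severe IBD patients achieved clinical and combined clinical and endoscopic remission (based on T2T definitions". SAP 8.1.3 defines failure to meet T2T goals only as absence of clinical and endoscopic remission, judged from investigator feedback and objective assessment.

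Surgery is handled elsewhere. Protocol 4.2 states: "IBD-related surgery will include but not be restricted to colectomy, ostomy (colostomy or ileostomy), fistula repair, abscess repair, and strictureplasty". Bowel resection is not named, but the list is open. Protocol 6.2, SAP 6.1 and SAP 8.1.3 give IBD-related surgery as an example of treatment failure. SAP 5.3.3 collects "IBD surgical treatment (indications, types of surgeries, complications, presence of stoma, etc" over the observation year.

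SAP 8.1.3 tabulates both remission and failure by the original treatment combination, meaning the first one recorded at the start of the two-year retrospective period. The tables are repeated by treatment pattern where the pattern is large enough.

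**The concern.** Take a CD patient whose ulcerated segment is resected during the study, whose pain and bowel symptoms then resolve, and who has no ulceration at a later endoscopy. Under Protocol 4.4 this patient has achieved clinical and combined remission. Under the failure outcome the same patient has failed therapy. Both results fall in the same column of the SAP 8.1.3 tables, under a regimen that may have been started up to two years before enrolment.

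Remission and T2T achievement are reported by therapy, and SAP 8.1.1 plans exploratory analyses of association between treatment patterns and outcomes. If surgery is more frequent under some patterns than others, their remission rates are not comparable. Treatment decisions are also split by whether T2T goals were met (SAP 8.1.3), so a drug stopped after resection could appear as de-escalation after reaching target.

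**Working it through.** **1. Is there a rule anywhere for remission after surgery?**

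| Place | What it covers | Separates remission before and after surgery? |
|---|---|---|
| Protocol 4.4 | Symptoms, endoscopy or imaging | No |
| Protocol 6.2; SAP 6.1 | Surgery as failure, in a separate outcome | No |
| Protocol 6.2, 15.2.2 | Outcomes split by remission status (only selected outcomes in 15.2.2) | Could show surgery among remitters, but not which came first |
| SAP 7.4 | Surgery in the two years before biologic prescription | No; does not cover surgery on therapy |
| SAP 8.1.3 | Surgical treatment as a disease-related T2T factor | No; association only |
| Protocol 15.1; SAP 8.6 | No exclusion for performance or data availability | No; these patients stay in |

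None of these sections scores remission as not achieved, censors it or reports it separately after surgery.

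**2. Where does the route to remission hold?**

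- CD, clinical remission: resolution of pain and bowel symptoms is enough. The route holds.
- CD, combined remission: endoscopy or imaging after surgery is also needed, and it is recorded only if done in routine practice (Protocol 12.2). The route holds for those examined.
- UC after colectomy: absence of rectal bleeding is not enough, because bowel habit must also have resolved and may stay altered. The Mayo endoscopic subscore may not be available. No rule says how to score this patient.

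**3. The plan's own precision, as a yardstick.** Protocol 15.4 assumes 2000 patients, 40% on biologics, 40% with CD and 10% drop-out:

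2000 × 0.40 × 0.40 = 320; 320 × 0.90 = 288.

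Half-width at a 50% failure rate = 1.96 × √(0.50 × 0.50 / 288) = 5.77 points, printed as ±5.8%. At 40% it is 5.66 points, giving 34.3 to 45.7%. Both match the protocol table. This precision is for the failure proportion and serves here only as a scale.

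**4. Size of the overstatement.** Let *s* be the share with such surgery on therapy before the visit, and *q* the share of those then scored in remission. With these patients kept in the denominator and counted as not in remission on the earlier therapy, the percentage falls by *s* × *q*. The documents give neither value. For clinical remission at Month 12, with 288 patients:

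| *s* (assumed) | *q* (assumed) | Surgery, patients | Then in remission, patients | Overstatement, points | Relative to 5.77 |
|---|---|---|---|---|---|
| 2% | 25% | 5.8 | 1.4 | 0.5 | 0.09 |
| 5% | 50% | 14.4 | 7.2 | 2.5 | 0.43 |
| 10% | 50% | 28.8 | 14.4 | 5.0 | 0.87 |
| 10% | 75% | 28.8 | 21.6 | 7.5 | 1.30 |

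**The case against.** The strongest reply is that the outcome is the percentage of patients who reach the target, not remission caused by a drug. Protocol 5.1 includes surgery in IBD treatment, and Protocol 15.2.4 says effectiveness cannot be fully evaluated in this design. Counting target achievement whatever happened on the way is a legitimate description. That stands as a reason to keep the unmodified rate. It does not justify presenting that rate by drug combination, beside a failure outcome that includes surgery, without saying which remissions followed an operation.

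Second, surgery is not unique. Escalation, switching and augmentation are also failures, and later remissions are likewise tabulated under the original combination. This is true. Resection differs because it can remove the tissue that the endoscopic criterion examines. The tables by pattern, with patterns re-assessed for months 0 to 6 and 6 to 12, ease attribution, but only where a pattern is large enough.

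Third, investigator feedback enters the T2T judgement and the eCRF records the nature of remission, so an investigator might judge otherwise. No rule requires it. The example tables in SAP section 9 were not available for this review, so a cross-tabulation there cannot be ruled out.

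A reader might infer that every UC patient after colectomy is scored in remission. The bowel-habit condition and the possibly missing endoscopic subscore do not support that. A reader might also infer that patients with a stoma at Visit 1 add to the overstatement. The direction is not established: liquid output could raise the Harvey-Bradshaw stool item (Protocol Appendix 4).

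**Conclusion.** The point holds as an attribution gap. As written, a remission after bowel resection counts towards the therapy that preceded it, most clearly for clinical remission in CD. For UC after colectomy the defect is that no scoring rule exists, not that remission is shown to be overstated.

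The size is unknown. The 0.5 to 7.5 points are illustrations under assumed values of *s* (2 to 10%) and *q* (25 to 75%), for clinical remission at Month 12. They should not be read as an estimate of bias, nor carried over to Month 6 or to combined remission. Only the top of the range exceeds the planned half-width of 5.8 points. The study is descriptive, so no test or sample size changes.

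A reader might conclude that every patient with surgery should be scored as not in remission from then on. The documents do not support so broad a rule: SAP 7.4 recognises biologic therapy given after surgery to prevent relapse in CD, and the rule would count against a drug started after the operation.

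**What to change.** In SAP 8.1.3:

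- Report clinical and combined remission and T2T achievement at Visits 2 and 3 in two rows: *remission without prior colectomy, bowel resection or new stoma*, and *remission after such surgery*.
- Do not count the second row as achievement on the therapy in use before the surgery. Attribute remission on a therapy started after surgery to that later therapy.
- Show the unmodified rate as a sensitivity analysis.
- For patients with a colectomy or stoma, treat as missing only those Mayo or Harvey-Bradshaw items that cannot be scored. Keep usable CD symptom, endoscopy and imaging data.

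Surgery type and presence of stoma are already collected by period between visits (SAP 5.3.3), which is enough to place surgery before a given visit. Surgery dates are not expressly listed there. The sponsor should confirm that the eCRF holds them, since ordering surgery against therapy start dates needs them.

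The cost is SAP wording, a little programming and a slightly less favourable on-therapy remission rate. SAP 8.5 already provides for documenting the change.

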5.1 Background

Inflammatory Bowel Disease (IBD) consists primarily of two chronic, often relapsing, immunologically-mediated gastrointestinal disorders: ulcerative colitis (UC) and Crohn's disease (CD). CD and UC are chronic gastrointestinal diseases characterized by an exacerbated inflammatory

cell infiltrate in the gut mucosal tissue. Currently IBD present one of the most urgent and complicated problems of gastroenterology. IBD results in irreversible structural and functional defect of intestine, finally leading to patient's incapacity [1, 2, 5].

IBD represents both medical and social challenge. Heterogeneity of clinical course, extra intestinal symptoms, severe complications together with increasing prevalence constitute high urgency of this disease. Ulcerative colitis and Crohn's disease are of chronic relapsing or continuous course, therefore long lasting treatment (including surgery in case of complications) is often required [1-12]. So, patient's life quality is greatly affected. IBD often causes disability and incapacity in young and middle-aged population, patients experience limitation of working and physical capacity, social activity decrease and emotional disturbances.

The primary goal of treating patients with IBD is to maximize long-term health-related quality of life through control of symptoms, prevention of structural damage, normalization of function and participation in social and work-related activities. A "Treat to Target" (T2T) strategy has been proposed as an optimized management approach for inflammatory bowel diseases [13, 14, 17, 18, 21].

Existing treatment methods show insufficient effectiveness. Aminosalicylates are only modestly effective; glucocorticoids can cause unacceptable adverse events and do not provide a benefit as maintenance therapy. Tumor necrosis factor (TNF) antagonists, although efficacious, may predispose patients to infections and other serious adverse reactions [3, 4, 6-10, 12, 28, 29]. Besides, a considerable portion of patients do not respond to the treatment with TNF-antagonists (primary non-responders) or will lose response to such therapies over time (secondary loss of response). New biological treatment medication Vedolizumab (Entyvio®) is the first and only gut selective biologic approved medication indicated for the treatment of adult patients with moderate to severe UC and CD, who have had an inadequate response with, lost response to, or were intolerant to either non-biological therapy or a tumor necrosis factor-alpha (TNF α) antagonists [15, 16, 25, 26].

5.2 Rationale

There is no accurate information on treatment patterns used in routine clinical practice for IBD patients in Russia and other CIS countries [3, 6-10, 12]. In connection with this, appropriateness of the large-scale investigation gathering information about disease characteristics, treatment patterns treatment responses and achievement of "Treat to Target" goals in IBD patients of Russia, Belarus and Kazakhstan is evident.

Better understanding of the IBD disease management will help to reveal the gaps, increase treatment goals awareness and improve medical care of patients. This will also allow better understanding of the clinical and economic burden and potential significant unmet need related to anti-TNF therapy in IBD in relative countries. The impact of sub-optimal therapy among IBD patients on health care resource utilization (HCRU) will also be investigated.

6 Study Objectives and outcomes

6.1 Study objectives

The purpose of this study is to collect information regarding the real life practice of moderate to severe inflammatory bowel disease (IBD) management in Russia, Belarus and Kazakhstan: to document treatment patterns, treatment outcomes in patients with IBD particularly on the use of available biologic therapies.

Primary objective:

- To characterize the treatment patterns associated with biologics agents use or non-biological therapy (i.e. 5-ASA, immunosuppressive agents (including azathioprine (AZA), 6-mercaptopurine (6-MP), methotrexate (MTX), cyclosporine A), corticosteroids) in patients with moderate to severe Ulcerative Colitis (UC) and moderate to severe Crohn's Disease (CD).

Secondary objectives:

- To characterize patients treated with biologics or/and non-biological treatment (i.e. 5-ASA, immunosuppressive agents (including azathioprine (AZA), 6-mercaptopurine (6-MP), methotrexate (MTX), cyclosporine A), corticosteroids) in terms of demographics, medical, and treatment histories;
- To evaluate and describe the implementation and achievement of Treat-to-target (T2T) goals in real-world clinical practice in moderate to severe IBD patients treated by biological and non-biological therapy during 2 years before enrolment and 1 year observational period after enrolment by treatment type 1) to assess the extent to which proposed Treat to Target goals are achieved in moderate to severe UC/CD patients 2) to describe how and when UC/CD disease activity is assessed 3) to evaluate the potential challenges to achieving T2T targets during routine care ;
- Establish the impact on healthcare resources utilization for patients with moderate to severe UC and CD

Safety Objective:

- To describe the incidence of real-world safety data occurred during 12-months treatment period within routine clinical practice by treatment type (biologics or non-biological IBD therapy) and treatment history (biologic treatment naïve or with prior biological treatment).

Exploratory objective:

- To assess TB in moderate to severe IBD patients receiving biologics and/or non-biological treatment.

6.2 Study outcomes

The following outcomes will be evaluated in this study separately for UC and CD patients, within each group for subgroups of patients on biologic and non-biological therapy. Study outcomes will be analysed separately for the patients achieved and not achieved clinical remission during the study.

Primary outcomes:

- Distribution of treatment patterns used in patients with moderate to severe UC and with moderate to severe CD treated with biologics. Treatment patterns will be evaluated within 2 years before enrolment – retrospective data and one year after enrolment- prospective data and will include name and type of drug (original product or biosimilar) and treatment regimen including modifications.
- Distribution of treatment patterns used in patients with moderate to severe UC and with moderate to severe CD treated with non-biological treatment. Treatment patterns will be evaluated within 2 years before enrolment – retrospective data and one year after enrolment- prospective data and will include treatment regimen including modifications.

Secondary outcomes:

- Distribution of socio-demographic variables in patients with moderate to severe UC/ CD treated with biologics or/and non-biological treatment.
- Distribution of clinical variables in patients with moderate to severe UC/ CD treated with biologics or/and non-biological treatment. Clinical characteristics include family history of IBD, smoking habits (no smoker, ex-smoker and current smoker), medical history comorbidities, disease characteristics (age of disease onset, location of disease, clinical course, disease severity, intestinal and systemic (extraintestinal) manifestations, complications in history and during the study observational period, etc.).
- Description of methods used for documentation of disease activity in routine practice (incl. clinical, endoscopic, lab, histological), and frequency of objective CD/UC disease activity assessment using different methods.
- Percentage of moderate to severe IBD patients achieved clinical and combined clinical and endoscopic remission (based on T2T definitions).
- Percentage of patients with moderate to severe IBD with at least one episode of failure of biological therapy or/and non-biological therapy (e.g., dose escalation of biologics, switching to another therapy, IBD-related surgery, medication augmentation).
- Patterns of treatment decisions\actions made after making the clinical assessment of IBD activity (incl. therapeutic de-escalation, escalation, without changes) depending on scenario of achievement /non-achievement of T2T treatment goals.

- Challenges of implementing a T2T strategy in UC and CD in real clinical practice (incl. clinicians related factors, patient related factors, disease related factors).
- Healthcare resources utilization for patients with moderate to severe UC/ CD: hospitalizations due to complications, IBD related surgeries, disability determination (frequency, percentage of UC and CD patients, who used these healthcare resources) within 2 years before enrolment and during 12-months observational period
- Percentage of UC and CD patients with surgical treatment in 2 years history and during 12-months observational period in frames of this study: indications, types of surgeries, complications

Safety outcome:

- Patient incidence and type of adverse drug reactions related to IBD treatment occurring during 12-months treatment period within routine clinical practice by treatment type (biologics or non-biological therapy) and treatment history (biologic treatment naïve or with prior biological treatment);
- Patient incidence and type of serious adverse events related to IBD treatment occurring during 12-months treatment period within routine clinical practice by treatment type (biologics or non-biological therapy) and treatment history (biologic treatment naïve or with prior biological treatment).

Exploratory outcomes:

- Number of moderate to severe UC and CD patients with TB positive tests results/active TB before start of biological therapy.
- Number of moderate to severe UC and CD patients with TB reactivation/occurrence in frames of this study by treatment type (biologics or/and non-biological treatment).

7 Study Administrative Structure

Contact and responsibilities of all parties contributing to the study, including all investigators, are detailed below.

The sponsor is responsible for all study-related activities including study set-up activities and study documentation development. The responsible CRO for specific study-related activities will perform these activities in full or in partnership with the sponsor.

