15.2.2. Statistical analysis methods

All data from patients enrolled in this study will be analyzed. Information on CD and UC patients will be presented separately. Also, analysis will be performed separately by therapy subgroups (patients receiving non-biological therapy and patients receiving biological therapy). Due to complexity of treatment regimen a manual review can be used to define treatment subgroup for each patient.

A descriptive analysis approach will be used to analyze the data and the study outcomes for the different study subgroups.

Descriptive statistics will include summary tables (n, mean, median, standard deviation, minimum and maximum, lower and upper quartile for continuous variables and n, frequency and percentage for categorical values). Proportion will be assessed together with 95% confidence interval, if applicable. Cross tabulations will be used to present study outcomes by the corresponding subgroups, when required. Time to event will be described with Kaplan-Meier estimates. Median time to event will be presented together with the lower and upper quartiles. Baseline and retrospective data will be used to describe the patient population and will be tabulated separately.

The number and percentage of patients who have reached remission while in the study will be presented. Selected outcomes will be reported separately for those who have reached remission and those who haven't.

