#### 8.1.3 Assessment of secondary and exploratory endpoints

**Each original treatment combination** (defined as the treatment combination that was used by the patient at the very start of retrospective observation period, i.e. first recorded treatment combination in the study) will be tabulated by the below listed parameters using the generic table format below (see example tables: Table 10, Table 11, Table 12 and Table 6):

- Demographic data;
- Disease activity at Visits 1, 2, 3 (Mayo, Harvey-Bradshaw indices);
- Disease status assessed by investigator at Visits 1, 2, 3;
- Frequency (percentage) of clinical, endoscopic and histologic remission at Visits 1, 2, 3 and retrospective period of observation;
- Extent of lesion at Visits 1, 2, 3;
- Systemic (extraintestinal) manifestations at Visits 1, 2, 3;
- Total number, duration and severity of disease exacerbations by Visit 1, 2 and 3;
- Total number, type and duration of disease complications by Visit 1, 2 and 3;
- Laboratory and instrumental assessments at Visits 1, 2, 3;
- Percentage of patient with surgical treatment by Visits 1, 2, 3 grouped by:
  - Indication;
  - Surgery type;
  - Presence of complications.
- Number of surgeries by Visits 1, 2, 3;

Protocol ID	MACS-2017-102279	STATISTICAL ANALYSIS PLAN	Page 25 of 41	
IP	N/A		Date	30.12.2021
ID	MACS-2017-102279_SAP		Version	v1.2 final

- Percentage of patients with at least one episode of failure or biological or/and non-biological therapy (e.g., dose escalation of biologics, switching to another therapy, IBD-related surgery, medication augmentation) by Visits 1, 2 and 3;
- Separately for patients who achieved / not achieved T2T treatment goals (based on the clinical assessment of IBD) by Visits 1, 2 and 3:
  - Presence of therapeutic de-escalation;
  - Presence of therapeutic escalation;
  - Continuation of therapy without any changes.
- Healthcare resources utilization:
  - Hospitalizations due to complications;
  - IBD-related surgeries;
  - Percentage of patients that used healthcare resources;
- Only for biological therapy - percentage (by Visits 1, 2, 3) of patients with:
  - Positive test results for TB before the start of biological therapy;
  - Active TB before the start of biological therapy;
- Percentage of patients by Visits 1, 2, 3 with:
  - Reactivation of TB;
  - New occurrence of TB.

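### Protocol 6.2 groups outcomes by remission reached during the study, with no landmark, so differences in events of the same 12 months can partly reflect event order and follow-up length

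*Protocol*

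**What the plan says.** Protocol 6.2, in the paragraph that introduces the primary, secondary and safety outcomes, states: "Study outcomes will be analysed separately for the patients achieved and not achieved clinical remission during the study". The study summary repeats it. Neither place limits which outcomes are meant.

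Protocol 15.2.2 is narrower: "Selected outcomes will be reported separately for those who have reached remission and those who haven't". It does not list the selection. It places the label after enrolment: "The number and percentage of patients who have reached remission while in the study will be presented". Protocol 4.4 gives the assessment times: "Treat to target approach achievement will be evaluated at observational (Month 6) and final (Month 12) visits".

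The SAP is narrower again. Its subgroup list (7.4) has no remission subgroup. The one split of this kind is in 8.1.3, "Separately for patients who achieved / not achieved T2T treatment goals", by Visits 1, 2 and 3, and it covers only de-escalation, escalation or no change of therapy.

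The outcomes within reach of the 6.2 sentence include treatment failure, with the examples "dose escalation of biologics, switching to another therapy, IBD-related surgery, medication augmentation", and also surgery, hospitalisation and adverse reactions during the 12 months. The primary outcome reaches further back: "Treatment patterns will be evaluated within 2 years before enrolment", plus one year after.

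No section fixes a landmark, treats remission as time-varying, or says in which column a patient with no remission assessment appears. Protocol 15.2.4 names attrition bias but not this issue.

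**The concern.** The label is set at Month 6 or Month 12. The events it would group run from Day 1 to Month 12. Two mechanisms follow.

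- **Order of events.** A treatment change in Months 0 to 6 counts as failure. It can also help bring about remission at Month 12, or mark active disease that makes remission less likely. The label is then partly a consequence of the outcome that it is used to divide.
- **Follow-up length.** A patient first seen in remission at Month 12 must have been followed to Month 12. A patient lost before Month 6 has little time in which an event could be recorded. If such patients are counted as non-remitters, that group has shorter follow-up and so fewer recorded events.

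At stake is the reading of the table. Protocol 5.2 says the effect of sub-optimal therapy on resource use will be investigated. A table of failures or admissions by remission invites the reading that remission goes with fewer (or more) such events, when the label alone can produce, enlarge or reverse the difference.

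**Working it through.** **Plan's own figure.** Protocol 15.4: 2000 × 0.4 × 0.4 = 320 CD patients on biologics; × 0.9 = 288. Half-width at 50% failure: 1.96 × √(0.25/288) = 5.8 points, as stated. The concern does not affect this figure.

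**Inputs.** From Protocol 15.4: 50% failure at 12 months (upper end of 40–50%) and 10% drop-out. Assumed, not in the documents: constant rates of both, and 30% remission at each of Months 6 and 12. Remission never affects later failure in this model.

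Monthly rates: λ = ln 2/12 = 0.05776 (failure), μ = −ln 0.9/12 = 0.00878 (drop-out). Then μ/(λ+μ) = 0.13195. With G(t) = exp(−(λ+μ)t), G(6) = 0.6708 and G(12) = 0.45. Among patients leaving between months a and b, with D = exp(−μa) − exp(−μb), observed failure is [D − 0.13195 × (G(a) − G(b))]/D.

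| Followed | Share | Observed failure |
|---|---|---|
| under 6 months (never assessed) | 1 − 0.9487 = 5.13% | (0.05132 − 0.04344)/0.05132 = 15.4% |
| 6 to 12 months | 0.9487 − 0.9 = 4.87% | (0.04868 − 0.02914)/0.04868 = 40.2% |
| 12 months | 90% | 50% |

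**1. Remission unrelated to failure.** Completers have remission at least once with probability 1 − 0.7² = 0.51; those leaving in Months 6 to 12, 0.30.
- Achieved: (0.9×0.51×0.5 + 0.0487×0.30×0.402)/(0.9×0.51 + 0.0487×0.30) = 0.2354/0.4736 = 49.7%.
- Not achieved, assessed patients only: 0.2342/0.4751 = 49.3%. Gap 0.4 points.
- Not achieved, with never-assessed patients added: (0.2342 + 0.0079)/(0.4751 + 0.0513) = 46.0%. Gap 3.7 points.
- Kaplan-Meier gives 50.0% in both groups here, because only censoring differs.

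**2. An early treatment change raises Month 12 remission from 30% to 50%.** Completers split into early failure 0.2929, later failure 0.2071, none 0.5. Early failures then have remission at least once with probability 1 − 0.7×0.5 = 0.65.
- Achieved: [0.9×(0.2929×0.65 + 0.2071×0.51) + 0.0059]/[0.9×(0.2929×0.65 + 0.7071×0.51) + 0.0146] = 0.2723/0.5105 = 53.3%.
- Not achieved, assessed only: 0.1973/0.4382 = 45.0%. Gap 8.3 points.
- With never-assessed patients added: 0.2052/0.4895 = 41.9%. Gap 11.4 points.

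**3. Recent failure lowers the chance of remission.** This was simulated with 1,000,000 patients per scenario: failure 40% or 50%; remission 30% or 50% per visit, multiplied by 1, 0.75, 0.5 or 0.25 after failure in the preceding 6 months; drop-out 0% or 10%; unobserved remission counted as not achieved. Failure in the not-achieved group minus the achieved group ran from −6.1 to +20.8 points. With 50% failure, 30% remission, multiplier 0.5 and 10% drop-out, the rates were 43.9% (achieved) and 50.5% (not achieved), the opposite sign to step 2.

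**4. Does a Month 6 landmark remove it?** Let early failure halve Month 6 remission (30% to 15%). Patients still failure-free make up 0.7071×0.30/(0.7071×0.30 + 0.2929×0.15) = 82.8% of Month 6 remitters and 0.7071×0.70/(0.7071×0.70 + 0.2929×0.85) = 66.5% of the others. Failure observed in Months 6 to 12 among failure-free patients is (1 − 0.13195) × (1 − 0.6708) = 28.6%.
- All patients present at Month 6 in the denominator: 0.828 × 28.6 = 23.7% against 0.665 × 28.6 = 19.0%, an artificial gap.
- Only patients failure-free at Month 6: 28.6% in both by construction (28.6% and 28.5% simulated). Across the step 3 scenarios this version stayed within ±0.2 points.

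**The case against.** **The split may be far smaller than 6.2 suggests.** A reader might infer from 6.2 alone that every outcome will be divided by remission at any time. The documents do not support that. Protocol 15.2.2 and the statistical part of the summary say selected outcomes, and the SAP splits only treatment decisions. Protocol 6.2 describes those as made after the activity assessment, so there the label comes first. The phrase at any time appears nowhere. This stands, and it narrows the point. It does not remove it: the unlimited sentence remains in force, and nothing excludes failure, surgery or safety.

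**Lost patients need not become non-remitters.** A reader might infer that a patient lost before Month 6 can only fall into the not-achieved group. The plan points the other way: percentages use non-missing observations (Protocol 15.2.1, SAP 8.1.1), unresolved data stay missing (SAP 8.4), and Protocol 15.2.4 says last data will be gathered for early leavers. On that reading the follow-up gap is 0.4 points, not 3.7. This also stands; what is missing is an explicit rule for this label. The SAP's example tables (section 9) were not in the text reviewed and may settle it.

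**The larger gaps are modelled, and the study is descriptive.** In steps 2 and 3 the link between treatment change and remission is real within the model, so a table showing it would be accurate as description. SAP 8.3 plans no tests, and the exploratory associations in SAP 8.1.1 concern treatment patterns, not remitters against non-remitters. This limits the severity. What remains wrong is reading such a gap as what follows remission, and nothing in the plan warns against that.

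**Conclusion.** The point holds in a limited form. Applied as written to events in the same 12 months, the 6.2 split mixes label and outcome, and no section prevents it. The follow-up part is small (0.4 points) under the plan's own missing-data conventions and 3.7 points otherwise. The order-of-events part can be larger and can take either sign: −6.1 to +20.8 points over the scenarios tried. Kaplan-Meier deals with the follow-up part only, because the grouping would still use later information.

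A reader might infer a known bias of a known direction. The documents give no remission rate and no link between failure and remission, so neither can be stated. Nor should the gaps be set directly against the planned ±5.8 points, which applies to a single proportion. If the 288 patients divided evenly, a difference between the halves would have a half-width of 1.96 × √(2 × 0.25/144) = 11.5 points. The smaller gaps would be lost in noise in that subgroup and matter more in larger ones.

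For fixed characteristics such as demographics, family history or age at onset, tabulation by later remission is legitimate description. The overall treatment-pattern tables are unaffected. This should be corrected, but it does not undermine the study.

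**What to change.** 1. Reconcile Protocol 6.2, Protocol 15.2.2 and SAP 8.1.3, and list the outcomes to be split by remission.
2. For prospective event outcomes, group by remission status at Visit 2. Count first events between Month 6 and Month 12 among patients still under observation and free of that event at Month 6, using Kaplan-Meier for censoring. The event-free restriction is needed: step 4 shows that a landmark without it can create a gap of its own. Treating remission as time-varying is an alternative.
3. Show patients with no remission assessment in a separate column.
4. Keep the during-study split only for baseline and retrospective descriptors, labelled descriptive.

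Cost: SAP wording and one re-cut of tables from dates already collected; no new data. Downside: events in Months 0 to 6, and remission first seen at Month 12, leave this split. Both stay in the overall tables.
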